6.12.1.2 Clinical Laboratory Parameters

All clinical laboratory parameters listed in Section 4.2.2 will be grouped by category and summarized by visit, with hematology, chemistry, urinalysis, and serology summarized separately. Absolute values and, where applicable, change from baseline for quantitative parameters will be summarized by the number of participants, mean, SD, median, minimum, and maximum values. Qualitative parameters will be summarized by absolute counts (n) and percentages (%). Percentages will be based on the number of participants with data.

Additionally, shift tables based on the NCI-CTCAE Version 5.0 toxicity grading scale will be presented for each laboratory parameter between pre-treatment and worst case on-treatment.

For parameters presenting both hyper- and hypo- NCI-CTCAE toxicities pre-treatment, both changes to lowest and highest on-treatment values will be presented as shift tables.

Additionally, an evaluation of drug-induced serious hepatotoxicity (eDISH) plots of max ALT versus max Bilirubin and max AST versus max Bilirubin will be produced by age cohort and overall. ALT/AST and Bilirubin will be displayed as multiple of the upper limit of normal (ULN) with lines denoting 2 x ULN for Bilirubin and 3 x ULN for ALT/AST.

Document: S:\Q_146\Q_03974\MEK-NF-201\Prog_Stat\Documentation\SAP\MEK-NF-201 SAP v1.0.0.docx

Author: Version 1.0.0, 02 Nov 2023

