5.2. Exclusion Criteria

Participants are excluded from the study if any of the following criteria apply:

Medical Conditions

1. Participant has a Screening alanine transaminase (ALT) value of > 2.0 x upper limit of normal (ULN);

- 2. Participant has a Screening total bilirubin value of $> 1.5 \times ULN$ (isolated bilirubin $> 1.5 \times ULN$ is acceptable if bilirubin is fractionated and direct bilirubin < 35%);
- 3. Participant has a history of malignancy associated hypercalcemia;
- 4. Participant has an active parathyroid disorder, hyperphosphatemia at Screening (serum phosphorus > 1 x ULN), or serum calcium (mg/dL) x serum phosphorus (mg/dL) product > 70 at Screening;
- 5. Any clinically significant active or known history of liver disease, or known hepatic or biliary abnormalities (with the exception of Gilbert's syndrome or asymptomatic gallstones);
 - 5.1. Hepatitis serology and viral load will be tested at Screening. Patients who are hepatitis B surface antigen (HBsAg) positive or hepatitis C virus (HCV) antibody positive at Screening must not be enrolled until further definite testing with hepatitis B virus (HBV) deoxyribonucleic acid (DNA) titers is < 500 IU/mL or HCV ribonucleic acid (RNA) polymerase chain reaction test is negative;
- 6. Lymphoma, leukemia, or any malignancy (including malignant glioma or MPNST) within the past 5 years except for basal cell or squamous epithelial carcinomas of the skin that have been resected with no evidence of metastatic disease for 3 years;
- 7. Breast cancer within the past 10 years;
- 8. Participants with evidence of an active optic glioma or other low-grade glioma, requiring treatment with chemotherapy or radiation therapy. Participants not requiring treatment are eligible. Ophthalmological findings secondary to long-standing optic pathway glioma (such as visual loss, optic nerve pallor or strabismus) or long-standing orbito-temporal PN (such as visual loss, strabismus) will NOT be considered a significant abnormality for the purposes of the study;
- 9. Participant has abnormal QT interval corrected by Fridericia's formula (> 450 msec for male participants, > 470 msec for female participants, or > 480 msec for participants with bundle branch block) (triplicate ECG readings taken approximately 2 to 3 minutes apart and averaged) at Screening;

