9.4.2. Safety Analyses

All safety analyses will be performed on the Safety Population.

Endpoint	Statistical Analysis Methods
Safety Endpoints	The safety and tolerability of mirdametinib (PD-0325901) will be evaluated by means of study drug-related adverse event reports, physical examinations, and laboratory safety evaluations. National Cancer Institute CTCAE Version 5.0 will be used for grading of adverse events. Investigators will provide their assessment as related to treatment (definite, probable, or possible relationship).
	The incidence of treatment-emergent adverse events, SAEs, adverse events of at least Grade 3 in severity, study drug-related adverse events, and adverse events leading to withdrawal of study drug will be summarized. Treatment-emergent adverse events will be those that start or worsen on or after the first day of study drug through 30 days after the last dose of study drug; related adverse events will be those with an Investigator determination of related to treatment.
	Laboratory data will be analyzed by summary statistics over time, as well as by shift tables based on NCI CTCAE Version 5.0 grades of severity. In addition, ECG intervals will be summarized by visit. The number and percentage of participants who have a post-Baseline QTcF between 450 and 480, > 480, and > 500, as well as the number and percentage of participants who have a change from Baseline in QTcF of < 30, 30 to 60, and > 60 will be summarized.

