4.2.2 Clinical Laboratory Evaluations

Blood and urine samples are collected and analyzed by a central laboratory. All laboratory results were standardized to Système International (S.I.) units. For all tables and figure summaries, only central laboratory data will be used. All data (including local laboratory data) will be included in listings.

In the case that multiple assessments map to the same visit, then the value at the scheduled assessment will be taken over any unscheduled assessments. If there are multiple unscheduled assessments, the assessment closest to the target study day will be used.

For the duration of the study, all safety laboratory assessments will be checked for abnormalities and measured against the NCI-CTCAE Version 5.0 for toxicities. The worst on-treatment assessment is determined by the value corresponding to the highest NCI-CTCAE Version 5.0 toxicity grade.

Hematology and biochemistry parameters with either a change of ≥ 2 in CTCAE Grade from baseline or a CTCAE Grade ≥ 4 will be flagged as markedly abnormal.

For the quantitative laboratory tests, the change from baseline value at each post-baseline visit will be calculated as the difference between the measurement obtained at the specific post-baseline visit and the baseline value.

In addition, quantitative test results at each visit will be categorized by the laboratory as 'Normal' (within the reference range) or 'Abnormal' (outside the reference range) according to the

Document: S:\Q_146\Q_03974\MEK-NF-201\Prog_Stat\Documentation\SAP\MEK-NF-201 SAP v1.0.0.docx
Author:

Statistical Analysis Plan

SpringWorks Therapeutics Protocol Number: MEK-NF-201

reference ranges specified in the laboratory manual. Abnormal results will be further classified as being 'Low' or 'High', depending on whether the result is below or above the reference range limits. For all abnormal values, clinical significance (as determined by the investigator) should be indicated.

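### Separate low and high laboratory shift tables hinge on toxicities seen before treatment, so other parameters graded both ways get one table that merges directions and understates cross-direction shifts

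*SAP*

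**What the plan says.** Protocol 9.4.2 sets the general plan: "Laboratory data will be analyzed by summary statistics over time, as well as by shift tables based on NCI CTCAE Version 5.0 grades of severity". It gives no rule on direction.

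SAP 6.12.1.2 says that the shift tables "will be presented for each laboratory parameter between pre-treatment and worst case on-treatment". SAP 4.2.2 defines the worst case: "The worst on-treatment assessment is determined by the value corresponding to the highest NCI-CTCAE Version 5.0 toxicity grade". Neither sentence mentions direction.

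The only directional rule for these tables is in SAP 6.12.1.2: "For parameters presenting both hyper- and hypo- NCI-CTCAE toxicities pre-treatment, both changes to lowest and highest on-treatment values will be presented as shift tables".

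SAP 4.2.2 also defines a flag for hematology and biochemistry parameters, under which "a change of ≥ 2 in CTCAE Grade from baseline or a CTCAE Grade ≥ 4 will be flagged as markedly abnormal". This rule does not mention direction either.

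Direction is recorded at the level of single values: "Abnormal results will be further classified as being 'Low' or 'High', depending on whether the result is below or above the reference range limits". No shift table is planned from that classification.

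**The concern.** A parameter needs two shift tables when it can be toxic in both directions. That is a property of the grading scale and is known in advance. The SAP makes it depend on whether both kinds of toxicity were present before treatment, which depends on who enrolled and says nothing about what the drug may do afterwards.

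A two-way parameter that misses the condition falls back to the single table, with three consequences:

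- High and low on-treatment toxicities of the same grade land in the same cell. This happens even when every baseline is normal.
- A participant with both a low and a high event on treatment contributes only the higher grade.
- A participant who starts abnormal on one side and crosses to the other has the baseline grade of the wrong direction subtracted from the apparent shift.

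Laboratory change is a named secondary safety endpoint, and the shift tables are the grade-based display that the protocol promises. By-visit means with minimum and maximum do not show how many participants developed a given grade in a given direction.

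**Working it through.** The documents give no figure on this point, so there is none to reproduce. The check applies the stated rules to grade combinations.

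**1. Rules applied.** The single table shows baseline grade to highest on-treatment grade, in either direction (SAP 4.2.2 and 6.12.1.2). A direction-specific table counts the opposite direction as Grade 0. For baseline low Grade b and worst on-treatment high Grade w:

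- single table: b to w, a shift of w − b;
- high-direction table: 0 to w, a shift of w;
- understatement: w − (w − b) = b.

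The understatement is the baseline grade, so it is zero for anyone at Grade 0.

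**2. Examples.** The high value is taken to be the worst-graded value on treatment.

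| Course | Single table | High-direction table | Flag as written |
|---|---|---|---|
| Grade 0 to high 2 | 0 to 2 | 0 to 2 | yes |
| Grade 0 to low 2 | 0 to 2 (same cell) | 0 to 0 | yes |
| Low 1 to high 1 | 1 to 1, no change | 0 to 1 | no |
| Low 2 to high 1 | 2 to 1, improvement | 0 to 1 | no |
| Low 1 to high 2 | 1 to 2 | 0 to 2 | no |
| Low 2 to high 3 | 2 to 3 | 0 to 3 | no |
| Low 1 to high 3 | 1 to 3 | 0 to 3 | yes |
| Low 2 to high 4 | 2 to 4 | 0 to 4 | yes |

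If the low 2 to high 1 participant is also low Grade 2 at some on-treatment visit, the single table shows 2 to 2 and the high event does not appear at all.

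**3. All cross-direction combinations, unweighted.**

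- Baseline low Grades 1 to 4 with on-treatment high Grades 1 to 4 give 4 × 4 = 16 combinations. The single table shows a fall in 6, no change in 4, a rise of one grade in 3, and a rise of two or more in 3. In the high direction, 12 of 16 rise by two or more.
- With baseline Grades 1 and 2 only, there are 2 × 4 = 8 combinations: a fall in 1, no change in 2, a rise of one in 2, and a rise of two or more in 3. In the high direction, 6 of 8 rise by two or more.
- Of those 6, the flag as written misses 3 (1 to 2, 2 to 2, 2 to 3) and catches 3 (1 to 3, 1 to 4, 2 to 4).

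These counts show what the rule can do. They are not frequencies.

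**4. Would the pre-treatment condition be met?** The documents give no baseline prevalence, so p is an assumption: each of n participants is independently low with probability p or high with probability p. The chance that both directions appear at least once is

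1 − 2(1 − p)^n + (1 − 2p)^n.

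| Assumed p per direction | n = 50 (one cohort) | n = 100 (both cohorts) |
|---|---|---|
| 0.5% | 0.05 | 0.15 |
| 1% | 0.15 | 0.40 |
| 2% | 0.40 | 0.75 |
| 5% | 0.85 | 0.99 |

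The SAP does not say whether the condition is judged per cohort or overall, so both columns are relevant. The answer runs from rarely met to nearly always met, depending entirely on p.

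**5. Eligibility.** Protocol 5.2 excludes "hyperphosphatemia at Screening (serum phosphorus > 1 x ULN") and also limits high glucose, so one direction can be largely absent before treatment for some parameters. Protocol 5.1 and 5.2 set no sodium or potassium limit. Calcium is restricted only through its product with phosphorus and a history of malignancy-associated hypercalcemia.

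**The case against.** The sentence may simply be loosely worded. Its subject is parameters, and the sentence before it uses pre-treatment as the starting point of the shift. The authors may have meant two tables for every parameter graded both ways. That is possible, but it is not what the text says, and a programmer following the text would produce a different set of tables. The ambiguity is itself a reason to correct it.

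Other planned outputs keep direction: the Low/High classification, listings of all laboratory data, by-visit values and changes with minimum and maximum, and adverse event tables by preferred term, since Protocol 8.2.5 requires clinically relevant laboratory changes to be recorded as adverse events. This stands, and it limits the defect to the shift tables and the flag. SAP 6.12.1.2 introduces the shift tables as an addition to the by-visit summaries, and it plans no table that uses the flag.

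A reader might infer that low-to-high swings will generally appear as little or no shift. The documents do not support that. Low Grade 1 to high Grade 3 is displayed as 1 to 3, which is understated but visible, and a participant at Grade 0 at baseline is shown with the right size of shift.

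A reader might also infer that the eligibility limits make the condition often unmet. That has support for phosphorus and glucose and in part for calcium, but none for sodium or potassium. The documents do not list which parameters are graded in both directions.

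**Conclusion.** The point holds as a defect in a stated rule. Under the literal reading, a two-way parameter that lacks either direction of toxicity before treatment gets one table. That table loses direction for all its on-treatment events and understates each cross-direction shift by exactly the baseline grade. The markedly abnormal flag has the same gap below Grade 4; Grade 4 and above is flagged whatever the baseline. No other section sets a direction rule for either.

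How often this would happen cannot be determined from the documents. The understatement needs a participant with a graded baseline abnormality who crosses to the opposite side. The merging of high and low events needs no baseline abnormality. The displays are descriptive, and no hypothesis test, decision rule or efficacy result depends on them.

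The conclusion rests on reading SAP 6.12.1.2 as written and on there being parameters graded in both directions, which that section itself presupposes.

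**What to change.** In SAP 6.12.1.2, replace the sentence containing the pre-treatment condition with:

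*For every parameter with both hyper- and hypo- CTCAE grades, shift tables from baseline to worst on-treatment grade are presented separately for each direction, counting the opposite direction as Grade 0.*

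In SAP 4.2.2, define the worst on-treatment grade and the markedly abnormal flag within each direction for those parameters, and say whether the two-grade change in the flag means a rise only. Listing the two-way parameters in the SAP would remove any remaining doubt.

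The cost is a few more tables and a small change to the derivation. No new data are needed.

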6.12.1.3 Electrocardiogram (ECG) Parameters

Absolute value and change from baseline for all ECG parameters as listed in Section 4.2.3 will be summarized by visit as per Section 5.1.2. Additionally, summaries will be provided by post-baseline visit for the following categories:

- Number (%) of participants with QTcF between 450 and 480
- Number (%) of participants with QTcF >480
- Number (%) of participants with QTcF >500
- Number (%) of participants with QTcF change from baseline <30
- Number (%) of participants with QTcF change from baseline between 30 and 60
- Number (%) of participants with QTcF change from baseline >60.

These summaries will be presented as per Section 5.1.2.

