7.1.2. QTc Stopping Criteria

If a clinically significant finding is identified (including, but not limited to changes from Baseline in QT interval corrected using Fridericia's formula [QTcF]) after first dose of study treatment, the Investigator or qualified designee will determine if the participant can continue in the study and if any change in participant management is needed. This review of the ECG printed at the time of collection must be documented. Any new clinically relevant finding should be reported as an AE.

A participant who meets either bulleted criterion based on the average of triplicate ECG readings will be withdrawn from study treatment:

- QTcF > 500 msec OR Uncorrected QT > 600 msec
- Change from Baseline of QTcF > 60 msec

Table 6 describes the discontinuation criteria for participants with underlying bundle branch block.

Table 6 Bundle Branch Block Discontinuation Criteria

Baseline QTcF with Bundle Branch Block	Discontinuation QTcF Threshold with Bundle Branch Block				
< 450 msec	> 500 msec				
450 to 480 msec	≥ 530 msec				

See the SoA (Section 1.3, Section 1.4) for data to be collected at the time of discontinuation and follow-up and for any further evaluations that need to be completed.

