5.6 Windowing Conventions

For safety data which are not linked to nominal visits (e.g. AEs) as per the protocol schedule of assessments, these data will be mapped to the cycle of treatment in which they onset according to Table 10 and Table 11.

For safety data collected at nominal visits, the recorded nominal visit will be used and unscheduled visits will be mapped to the nearest planned visit where it would be expected to be recorded, by study visit day, as per the protocol. If a record is mapped to a visit which has a valid reading nominally assigned, the nominally assigned visit value will be used in all summaries and analysis.

Table 10: Visit Windows – Treatment Phase

Assessment Study Day	Visit	Visit Label	Study Visit Day
	Screening	Screening	-45
2≤Sday<8	Cycle 1 – Week 1 (Baseline, study visit day 1)	C1D1	1
8≤Sday<29	Cycle 1 - Week 3 (Cycle Day 15)	C1D15	15
29≤SDay<57	Cycle 2 - Week 7 (Cycle Day 15)	C2D15	43
57≤SDay<85	Cycle 3 - Week 11 (Cycle Day 15)	C3D15	71
85≤SDay<113	Cycle 4 – Week 15 (Cycle Day 15)	C4D15	99
113≤SDay<141	Cycle 5 - Week 19 (Cycle Day 15)	C5D15	127
141≤SDay<169	Cycle 6 - Week 23 (Cycle Day 15)	C6D15	155
169≤SDay<197	Cycle 7 - Week 27 (Cycle Day 15)	C7D15	183
197≤SDay<225	Cycle 8 - Week 31 (Cycle Day 15)	C8D15	211
225≤SDay<253	Cycle 9 - Week 35 (Cycle Day 15)	C9D15	239
253≤SDay<281	Cycle 10 – Week 39 (Cycle Day 15)	C10D15	267
281≤SDay<309	Cycle 11 - Week 43 (Cycle Day 15)	C11D15	295
309≤SDay<337	Cycle 12 - Week 47 (Cycle Day 15)	C12D15	323
337≤SDay<365	Cycle 13 - Week 51 (Cycle Day 15)	C13D15	351
365≤SDay<393	Cycle 14 - Week 55 (Cycle Day 15)	C14D15	379

Document: S:\Q_146\Q_03974\MEK-NF-201\Prog_Stat\Documentation\SAP\MEK-NF-201 SAP v1.0.0.docx

Author:

	Safety Follow-up = 30 days after last dose	SFU	-
645≤SDay<673	Cycle 24 - Week 95 (Cycle Day 15)	C24D15	659
617≤SDay<645	Cycle 23 – Week 91 (Cycle Day 15)	C23D15	631
589≤SDay<617	Cycle 22 - Week 87 (Cycle Day 15)	C22D15	603
561≤SDay<589	Cycle 21 – Week 83 (Cycle Day 15)	C21D15	575
533≤SDay<562	Cycle 20 – Week 79 (Cycle Day 15)	C20D15	547
505≤SDay<533	Cycle 19 - Week 75 (Cycle Day 15)	C19D15	519
477≤SDay<505	Cycle 18 – Week 71 (Cycle Day 15)	C18D15	491
449≤SDay<477	Cycle 17 - Week 67 (Cycle Day 15)	C17D15	463
421≤SDay<449	Cycle 16 – Week 63 (Cycle Day 15)	C16D15	435
393≤SDay<421	Cycle 15 – Week 59 (Cycle Day 15)	C15D15	407

Abbreviations: SDay: study day for individual participant

Table 11: Visit Windows - LTFU Phase

Assessment Study Day	Visit	Visit Label	Study Visit Day

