6.12.1.4 Echocardiogram

Absolute values and change from baseline in LVEF will be summarized by visit as per Section 5.1.2. Additionally, shift tables based on the NCI-CTCAE Version 5.0 toxicity grading scale will be presented for LVEF between pre-treatment and worst case on-treatment.

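### SAP 6.12.1.3 tabulates the QTcF categories only by visit, so the participant-level counts that Protocol 9.4.2 appears to ask for cannot be obtained from the planned tables

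*SAP*

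**What the plan says.** Protocol 9.4.2 treats ECG data in two sentences. The first reads "In addition, ECG intervals will be summarized by visit". The next sets out the categorical summary: "The number and percentage of participants who have a post-Baseline QTcF between 450 and 480, > 480, and > 500", followed by "the number and percentage of participants who have a change from Baseline in QTcF of < 30, 30 to 60, and > 60". The by-visit qualifier appears only in the first.

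SAP 6.12.1.3 summarizes absolute values and changes for the ECG parameters by visit, then adds that "summaries will be provided by post-baseline visit for the following categories". The list that follows contains the protocol's six categories. No row or table is planned for a participant's maximum, worst or any-time value. SAP 7.1, which lists changes from the protocol's analyses, does not mention QTcF.

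Two other SAP sections bear on the point:

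- SAP 5.6, on safety data collected at nominal visits: "If a record is mapped to a visit which has a valid reading nominally assigned, the nominally assigned visit value will be used". An unscheduled ECG is mapped to the nearest planned visit and yields to the scheduled reading there.
- SAP 6.12.1.4, on LVEF: "shift tables based on the NCI-CTCAE Version 5.0 toxicity grading scale will be presented for LVEF between pre-treatment and worst case on-treatment". SAP 6.12.1.2 plans the same kind of worst-case table for laboratory parameters.

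**The concern.** A by-visit table answers how many participants are above a cut-off at a given visit. The protocol's sentence most naturally asks how many participants were above it during the post-baseline period. The answers differ whenever different participants are affected at different visits, and then the second figure is larger.

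The participant is also the unit on which the study acts. Protocol 7.1.2 states "A participant who meets either bulleted criterion based on the average of triplicate ECG readings will be withdrawn from study treatment", the criteria being QTcF above 500 msec (or uncorrected QT above 600 msec) or a QTcF rise above 60 msec, with separate thresholds for bundle branch block. Protocol 10.1.7 lists a single participant meeting the QTc criteria among the reasons for suspending or terminating enrollment.

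At stake is a safety summary, in a study the protocol calls potentially registrational, that seems to be specified in the protocol but is not produced by the SAP and not declared as changed. The primary endpoint is unaffected.

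**Working it through.** Neither document states a QTcF incidence, so there is no figure to reproduce. The check is a comparison of the texts and an illustration of what by-visit tables can and cannot determine.

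**Comparison**

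| Item | Protocol 9.4.2 | SAP 6.12.1.3 |
|---|---|---|
| ECG intervals | By visit | By visit |
| QTcF 450–480, > 480, > 500 | Participants with such a post-baseline value; no visit qualifier | By post-baseline visit |
| QTcF change < 30, 30–60, > 60 | Participants with such a change; no visit qualifier | By post-baseline visit |
| Maximum or worst value per participant | Not named, but the natural reading | None |
| Change declared in SAP 7.1 | – | No |

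**Inputs**

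- k = 8 scheduled Treatment Phase ECG visits after C1D1, from the schedule in Protocol 1.3: C1D15, C2D15, C5, C9, C13, C17, C21 and C24. The early termination, safety follow-up and LTFU ECGs are extra and not counted.
- The C1D1 post-dose ECG is also left out. SAP 4.2 defines baseline as the latest assessment on or before the treatment start date, so it is doubtful that this recording counts as a post-baseline visit.
- n = 50 per age cohort, 100 in total (Protocol 9.2).
- p = proportion exceeding a cut-off at each visit. The documents give no value; 0.5%, 1% and 2% are assumptions. Every participant is taken to have an ECG at every visit.

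**Formulas**

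For the same by-visit figure p, the participant-level incidence is:

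- p, if the same participants exceed at every visit;
- 1 − (1 − p)^k, if visits are independent;
- k × p, if different participants exceed at each visit.

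**Results for k = 8**

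| Assumed p | Same participants | Independent visits | Different participants |
|---|---|---|---|
| 0.5% | 0.5% | 1 − 0.995^8 = 3.9% | 8 × 0.5% = 4.0% |
| 1% | 1% | 1 − 0.99^8 = 7.7% | 8 × 1% = 8% |
| 2% | 2% | 1 − 0.98^8 = 14.9% | 8 × 2% = 16% |

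In counts: if one participant in a cohort of 50 exceeds a cut-off at each of the 8 visits, every by-visit table shows 1/50 = 2%. The same set of tables fits 1/50 = 2% of participants ever exceeding, 8/50 = 16%, and anything between.

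**Unscheduled recordings**

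If an excursion is seen only on an unscheduled ECG, and the visit to which it maps has a valid scheduled reading, SAP 5.6 uses the scheduled value. The excursion is then absent from the QTcF tables altogether, so even adding up the visit counts could miss it.

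**The case against.** **The protocol does not literally ask for this.** It does not say any, maximum or worst; the sentence follows one about by-visit summaries; and Protocol 9.4 calls itself a summary and leaves detail to the SAP. This stands in part. At-least-once counting is an inference, though the better one, because the visit qualifier is attached only to the intervals. A reader might infer a flat contradiction; the documents support an unreconciled difference.

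**Cases will be visible elsewhere.** Under Protocol 7.1.2, new clinically relevant ECG findings are reported as adverse events. SAP 6.12.1.1 counts these per participant, including those leading to discontinuation; SAP 4.3.1 tabulates reasons for discontinuation; and the by-visit statistics include the maximum. It would therefore be wrong to infer that QTcF excursions go unreported. But adverse event capture depends on the investigator's judgement, and a visit maximum shows that someone crossed a cut-off, not how many did. None of these outputs gives the number of participants in each category.

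**Withdrawal makes the visit counts nearly additive.** If participants leave treatment after crossing 500 msec or rising by more than 60 msec, each may be counted about once, and the loss is smallest for the most serious categories. This is fair. It does not help for 450–480, for values above 480 up to 500, or for rises of 30 to 60, which do not meet the general criteria in Protocol 7.1.2. Nor is it exact for the top categories: ECGs are also scheduled at early termination and safety follow-up, so one participant can appear more than once, and an unscheduled reading may not appear at all.

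**QT prolongation is not a listed risk.** Correct: it is absent from the benefit/risk section (Protocol 2.3) and from the adverse events of special interest. It is a stopping criterion, and the point rests on that alone.

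**The laboratory and LVEF tables create no obligation for QTcF.** Also correct. They show only that a worst-case summary is already within the SAP's usual practice.

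**Conclusion.** The point holds. The SAP gives the six QTcF categories only by visit, the protocol's wording most naturally calls for a count per participant, and the difference is not declared. The participant-level incidence cannot be recovered from the planned QTcF tables.

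The size is an interval, not an estimate. Over 8 visits the participant-level figure lies between 1 and 8 times the by-visit figure, depending on how far the same participants recur. A reader might infer that the tables understate the incidence about eightfold. That is only the upper end; if the same participants exceed repeatedly, there is no understatement. The documents do not say where in the range the study would fall, and the per-visit rates, the independent-visits case and complete attendance are all assumptions.

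This is a should-fix matter for safety reporting. It has no bearing on the primary efficacy analysis or on the stopping rules themselves, which operate during the study without reference to these tables.

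**What to change.** In SAP 6.12.1.3, add a table by age cohort giving the number (%) of participants by maximum post-baseline averaged QTcF (450–480, > 480, > 500) and by maximum increase from baseline (< 30, 30–60, > 60). Use all post-baseline ECGs, and state that unscheduled recordings are included despite the SAP 5.6 rule. Classifying by the maximum also gives the < 30 category a clear meaning, since most participants could have some change below 30 at one visit or another. Keep the by-visit table alongside.

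If the sponsor intends by-visit counts only, SAP 7.1 should say so. That would make the change transparent but would not supply the participant-level figure.

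The cost is one derived table from data already collected. The percentages may look less favourable than the by-visit ones.
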